#### Bone lesions

- Bone scan, positron emission tomography (PET) scan or plain films are not considered adequate imaging techniques to measure bone lesions. However, these techniques can be used to confirm the presence or disappearance of bone lesions.
- Lytic bone lesions or mixed lytic-blastic lesions, with identifiable soft tissue components, that can be evaluated by cross sectional imaging techniques such as CT or MRI, can be considered as measurable lesions if the soft tissue component meets the definition of measurability described above.

• Blastic bone lesions are non-measurable.

#### Cystic lesions

- Lesions that meet the criteria for radiographically defined simple cysts should not be considered as malignant lesions (neither measurable nor non-measurable) since they are, by definition, simple cysts.
- Cystic lesions thought to represent cystic metastases can be considered as measurable lesions, if they meet the definition of measurability described above. However, if non-cystic lesions are present in the same patient, these are preferred for selection as target lesions.

#### Lesions with prior local treatment

• Tumor lesions situated in a previously irradiated area, or in an area subjected to other loco-regional therapy, are usually not considered measurable unless there has been demonstrated progression in the lesion.

#### Solitary lesions

• If a measurable disease is restricted to a solitary lesion, its neoplastic nature should be confirmed by cytology/histology.

### **Recording Tumor Measurements**

All measurable lesions up to a maximum of 2 lesions per organ and up to 5 in total and representative of all involved organs should be identified as target lesions and measured and recorded at baseline and at the stipulated intervals during treatment. Target lesions should be selected on the basis of their size (lesions with the longest diameters) and their suitability for accurate repetitive measurements (either by imaging techniques or clinically).

The longest diameter will be recorded for each target lesion. The sum of the longest diameter of all target lesions will be calculated and recorded as the baseline sum diameter to be used as reference to further characterize the objective tumor response of the measurable dimension of the disease during treatment.

One (1) exception to the above described approach is related to pathological lymph nodes. Pathological lymph nodes are defined as measurable lesions and may be identified as target lesions if the criterion of a short axis of  $\geq 15$  mm by CT scan is met. Only the short axis of these nodes will contribute to the baseline sum. Nodal size is normally reported as 2 dimensions in the plane in which the image is obtained (for CT scan this is almost always the axial plane; for MRI the plane of acquisition may be axial, sagittal or coronal). The smaller of these measures is the short axis.

A sum of the diameters (longest for non-nodal lesions, short axis for nodal lesions) for all target lesions will be calculated and reported as the baseline sum diameters. The baseline sum diameters will be used as reference to further characterize any objective tumor regression in the measurable dimension of the disease.

All other lesions (or sites of disease) should be identified as non-target lesions and should also be recorded at baseline. Measurements are not required and these lesions should be followed as "present", "absent", or in rare cases "unequivocal progression". In addition, it is possible to record multiple non-target lesions involving the same organ as a single item on the CRF (eg, "multiple enlarged pelvic lymph nodes" or "multiple liver metastases").

#### **Definition of Tumor Response**

#### Target Lesions

Response in target lesions is defined as follows:

- CR: disappearance of all target lesions.
- PR: at least a 30% decrease in the sum of diameters of target lesions, taking as reference the baseline sum diameters.
- PD: at least a 20% increase in the sum of diameters of target lesions, taking as reference the smallest sum on study (this includes the baseline sum if that is the smallest on study). In addition to the relative increase of 20%, the sum must also demonstrate an absolute increase of at least 5 mm. The appearance of 1 or more new lesions is also considered a sign of progression.
- Stable disease (SD): neither sufficient shrinkage to qualify for PR nor sufficient increase to qualify for PD, taking as reference the smallest sum diameters while on study.

When nodal disease is included in the sum of target lesions and the nodes decrease to "normal" size (<10 mm), they may still have a measurement reported on scans. This measurement should be recorded even though the nodes are normal in order not to overstate progression should it be based on increase in size of the nodes. As noted earlier, this means that patients with CR may not have a total sum of "0" on the CRF.

#### Non-Target Lesions

While some non-target lesions may actually be measurable, they need not be measured and instead should be assessed only qualitatively at the time points specified in the protocol.

Response in non-target lesions is defined as follows:

• CR: disappearance of all non-target lesions and normalization of tumor marker level. All lymph nodes must be non-pathological in size (<10 mm short axis).

- Non-CR/Non-PD: persistence of one or more non-target lesion(s) and/or maintenance of tumor marker level above the normal limits.
- PD: unequivocal progression of existing non-target lesions. (Note: the appearance of one or more new lesions is also considered progression).

### Cytology, Histology

These techniques can be used to differentiate between PR and CR in rare cases if required by protocol (for example, residual lesions in germ cell tumors). When effusions are known to be a potential adverse effect of treatment (eg, taxane compounds or angiogenesis inhibitors), the cytological confirmation of the neoplastic origin of any effusion that appears or worsens during treatment can be considered if the measurable tumor has met criteria for response or stable disease in order to differentiate between response or SD and PD.

For patients having effusions or ascites, only cases having cytological proof of malignancy should be recorded on the CRF. Effusions that have not been evaluated using cytology or were found to be non-malignant should not be recorded on the CRF.

### New Lesions

The appearance of new malignant lesions indicates PD. New lesion should be unequivocal (eg, not attributable to differences in imaging technique, or change in imaging modality or findings not attributable to tumor). If a new lesion is equivocal, for example due to its small size, continued therapy and follow-up assessment will clarify the etiology of the disease. If repeat scans confirm there is definitely a new lesion, then progression should be declared using the date of the initial scan.

The use of fluorodeoxyglucose (FDG)-PET is sometimes reasonable to complement a CT scan assessment of a PD (particularly for possible "new" disease). New lesions on the basis of FDG-PET imaging can be identified according to the following algorithm:

- Negative FDG-PET at baseline, with a positive FDG-PET at follow-up.
- No FDG-PET at baseline and a positive FDG-PET at follow- up: if the positive FDG-PET at follow-up corresponds to a new site of disease confirmed by CT, this is PD.

If the positive FDG-PET at follow-up is not confirmed as a new site of disease on CT, additional follow-up CT scans are needed to determine if there is truly progression occurring at that site (if so, the date of PD will be the date of the initial abnormal FDG-PET scan).

If the positive FDG-PET at follow-up corresponds to a pre-existing site of disease on CT that is not progressing on the basis of the anatomic images, this is not PD.

#### **Confirmation of Tumor Response**

Confirmation of response is required for non-randomized trials with primary endpoint of response, but is not required in randomized studies since the control arm serves as appropriate means of interpretation of data.

#### **Determination of Overall Response by RECIST Version 1.1**

When both target and non-target lesions are present, individual assessments will be recorded separately. The overall assessment of response will involve all parameters as depicted in Table 5.

Target Lesions	Non-Target Lesions	New Lesions	Overall Response
CR	CR	No	CR
CR	Non-CR/non-PD	No	PR
CR	Not evaluated	No	PR
PR	Non-PD or not all evaluated	No	PR
SD	Non-PD or not all evaluated	No	SD
Not all evaluated	Non-PD	No	NE
PD	Any	Yes or No	PD
Any	PD	Yes or No	PD
Any	Any	Yes	PD

#### Table 5. Response Evaluation Criteria in Solid Tumors

Abbreviations: CR=complete response, PR=partial response, SD=stable disease, PD=progressive disease, NE=none-evaluable

### **Best Overall Response**

The best overall response is determined once all the data for the patient is known. Best response in trials in which confirmation of CR or PR is not required (ie, randomized trials) is defined as the best response across all time points (for example, a patient who has SD at first assessment, PR at second assessment, and PD on last assessment has a best overall response of PR). When SD is believed to be the best response, it must also meet the protocol-specified minimum time from baseline. If the minimum time is not met when SD is otherwise the best time point response, the patient's best response depends on the subsequent assessments. For example, a patient who has SD at first assessment, PD at second and does not meet minimum duration for SD, will have a best response of PD. The same patient lost to follow-up after the first SD assessment would be considered non-evaluable.

When confirmation of CR and PR is required (ie, non-randomized trials with primary endpoint of response), the best overall response is defined according to the tumor response along the study. CR or PR may be claimed only if the criteria for each are met at a following time point as specified in the protocol (generally 4 weeks later).

Patients with a global deterioration of health status requiring discontinuation of treatment without objective evidence of disease progression at that time should be reported as "symptomatic deterioration". Every effort should be made to document objective progression even after discontinuation of treatment. Symptomatic deterioration is not a descriptor of an objective response: it is a reason for stopping study therapy. The objective response status of such patients is to be determined by evaluation of target and non-target lesions.

In some circumstances it may be difficult to distinguish residual disease from normal tissue. When the evaluation of CR depends upon this determination, it is recommended that the residual lesion be investigated (fine needle aspirate/biopsy) before assigning a status of complete response. FDG-PET may be used to upgrade a response to a CR in a manner similar to a biopsy in cases where a residual radiographic abnormality is thought to represent fibrosis or scarring.

### Appendix 4. ECG Findings of Potential Clinical Concern

#### ECG Findings That May Qualify as AEs

- Marked sinus bradycardia (rate <40 bpm) lasting minutes.
- New PR interval prolongation >200 msec.
- New prolongation of QTcF to >470 msec (absolute) or by  $\geq$ 60 msec from baseline.
- New onset atrial flutter or fibrillation, with controlled ventricular response rate, ie, rate <120 bpm.
- New onset Type I second-degree (Wenckebach) AV block of >30 seconds' duration.
- Frequent PVCs, triplets, or short intervals (<30 seconds) of consecutive ventricular complexes.

#### ECG Findings That May Qualify as SAEs

- QTcF prolongation >500 msec.
- New ST-T changes suggestive of myocardial ischemia.
- New onset left bundle branch block (QRS >120 msec).
- New onset right bundle branch block (QRS >120 msec).
- Symptomatic bradycardia.
- Asystole:
  - In awake, symptom-free participants in sinus rhythm, with documented periods of asystole ≥3.0 seconds or any escape rate <40 bpm, or with an escape rhythm that is below the AV node.
  - In awake, symptom-free participants with atrial fibrillation and bradycardia with 1 or more pauses of at least 5 seconds or longer.
  - Atrial flutter or fibrillation, with rapid ventricular response rate: rapid = rate >120 bpm.
- Sustained supraventricular tachycardia (rate >120 bpm) ("sustained" = short duration with relevant symptoms or lasting >1 minute).
- Ventricular rhythms >30 seconds' duration, including idioventricular rhythm (rate <40 bpm), accelerated idioventricular rhythm (40< x <100), and monomorphic/polymorphic ventricular tachycardia >100 bpm (such as torsades de

pointes).

- Type II second-degree (Mobitz II) AV block.
- Complete (third-degree) heart block.

#### ECG Findings That Qualify as SAEs

- Change in pattern suggestive of new myocardial infarction.
- Sustained ventricular tachyarrhythmias (>30 seconds' duration).
- Second- or third-degree AV block requiring pacemaker placement.
- Asystolic pauses requiring pacemaker placement.
- Atrial flutter or fibrillation with rapid ventricular response requiring cardioversion.
- Ventricular fibrillation/flutter.
- At the discretion of the Investigator, any arrhythmia classified as an adverse experience.

The enumerated list of major events of potential clinical concern are recommended as "alerts" and not to be considered as all inclusive of what to be reported as AEs/SAEs.

Abbreviations: AE=adverse event; AV=atrioventricular; ECG=electrocardiogram; PVC=premature ventricular complex; QTcF=QT interval calculated using Fridericia's correction factor; SAE=serious adverse event.

Score	Definition
0	Fully active, able to carry on all pre-disease performance without restriction.
1	Restricted in physically strenuous activity but ambulatory and able to carry out work of a light or sedentary nature, eg, light house work or office work.
2	Ambulatory and capable of all self-care but unable to carry out any work activities. Up and about more than 50% of waking hours.
3	Capable of only limited self-care, confined to bed or chair more than 50% of waking hours.
4	Completely disabled. Cannot carry on any self-care. Totally confined to bed or chair.
5	Dead

# Appendix 5. ECOG Classification of Performance Status

### **Appendix 6. Clinical Laboratory Tests**

The laboratory tests detailed in Table 6 will be performed by the local laboratory and must be performed in fasted condition. Investigators must document their review of each laboratory safety report.

Pregnancy testing:

- Refer to Section 4.1 Inclusion Criteria for screening pregnancy criteria.
- For details of timing of recommended pregnancy testing see Section 7.2.5.

Hematology	Clinical Chemistry 	Other Tests
Platelet count	BUN or urea	Highly sensitive serum or urine hCG
Hemoglobin	Creatinine	pregnancy test (as needed for women of
WBC count with differential:	Glucose (fasting)	childbearing potential).
Neutrophils 	Uric acid	Lipids: total cholesterol, LDL,  HDL,
Lymphocytes 	Potassium	and triglycerides.
Monocytes 	Sodium	
Eosinophils 	Total calcium	
Basophils 	Magnesium	
	AST	
	ALT	
	Alkaline phosphatase	
	Albumin	
	Total bilirubin	
	Phosphorus or phosphate	
	Serum total amylase 	
	Serum lipase	

 Table 6
 Protocol Required Safety Laboratory Assessments

Abbreviations: ALT=alanine aminotransferase; AST=aspartate aminotransferase; BUN=blood urea nitrogen; CRF=case report form; hCG=human chorionic gonadotropin; HDL=high-density lipoprotein; INR=international normalized ratio; LDL=low-density lipoprotein; SAE=serious adverse event; ULN=upper limit of normal; WBC=white blood cell; WOCBP=woman of childbearing potential.

- All events of ALT ≥3 × ULN and bilirubin ≥2 × ULN (>35% direct bilirubin) or ALT ≥3 × ULN and INR >1.5, if INR measured which may indicate severe liver injury (possible Hy's Law), must be reported as an SAE.
- 2. Values in percentages (%) are acceptable.
- 3. Pancreatic isoenzyme required if serum total amylase not within normal limits per local institutional ranges.
- 4. A measured LDL value is preferable instead of calculated LDL. If LDL value is calculated from Friedewald equation, this can be considered only in absence of the following circumstances: plasma dysbetalipoproteinemia (Type III hyperlipoproteinemia).

1. VERSION HISTORY

This Statistical Analysis Plan (SAP) for study B7461030 is based on the protocol version 1 dated 30Mar2020.

Table 1. Summary of Changes

Version/ Date	Associated Protocol Amendment	Rationale	Specific Changes
1/ 03 June 2020	Original 30 March 2020	N/A	N/A

2. INTRODUCTION

This SAP provides the detailed methodology for summary and statistical analyses of the data collected in Study B7461030. This document may modify the plans outlined in the protocol; however, any major modifications of the primary endpoint definition or its analysis will also be reflected in a protocol amendment.

Any deviations from this analysis plan will be described in the Clinical Study Report.

All summaries and analyses will include all data in the database at the end of the study which is defined as 1 year after the last participant first visit date in the study.

2.1. Study Objectives, Endpoints, and Estimands

Objective	Estimands Endpoints		
Primary			
To evaluate the safety and tolerability of single-agent lorlatinib in participants with unresectable advanced and/or recurrent ALK-positive Non-Small Cell Lung Cancer (NSCLC) with resistance or intolerance to at least 1 prior ALK inhibitor treatment.	• The primary estimand is the incidence of Adverse Events (AEs) from the time of first dose to at most 35 days post last dosing date or the date of initiation of a new anticancer therapy for all participants who receive at least 1 dose of lorlatinib, regardless of dosing interruptions or dosing compliance.	Incidence of AEs.	
Secondary	•		
To evaluate overall and intracranial antitumor activity of single-agent lorlatinib in participants with unresectable advanced and/or recurrent ALK-positive NSCLC with resistance or intolerance to at least 1 prior ALK inhibitor treatment.	• The secondary estimand is the treatment effect of lorlatinib as assessed by the investigator from time of first dose (Objective Response Rate (ORR) and Intra Cranial-Objective Response Rate (IC-ORR)) or time of first response (Duration of Response (DoR) and Intracranial Duration of Response (IC-DoR)) until progression is met, death or subsequent anticancer therapy is administered for all participants who receive at least 1 dose of lorlatinib without regard to tolerability or discontinuation from treatment.	Confirmed ORR, confirmed IC-ORR, DoR and IC-DoR as assessed by the Investigator using Response Evaluation Criteria in Solid Tumors (RECIST) version 1.1.	

2.1.1. Primary Estimand

The primary estimand is the incidence of Adverse Events from the time of first dose to 35 days post last dosing date or the date prior to initiation of a new anticancer therapy, whichever occurs first for all participants who receive at least one dose of lorlatinib, regardless of dosing interruptions or dosing compliance. It includes the following 4 attributes:

 Population: Participants with unresectable advanced and/or recurrent ALK-positive NSCLC with resistance or intolerance to at least 1 prior ALK inhibitor treatment as defined by the inclusion and exclusion criteria, and who receive at least one dose of Lorlatinib

- Variable: Binary indicator of whether any AE occurring at least once
- Intercurrent event: All data after the intercurrent event "initiation of a new anticancer therapy (-1 day)" or "treatment discontinuation (+35 days post last dosing date)" will be excluded. Dosing interruptions or dosing compliance are not considered as intercurrent event for this analysis..
- Population-level summary: Adverse event incidence rate from the time of first dose to 35 days post last dosing date or the date prior to initiation of a new anticancer therapy, whichever occurs first. AE incidence rate is the number of patients with any AE occurring at least once in the study population.

2.1.2. Secondary Estimands

A secondary estimand is the treatment effect of Lorlatinib as assessed by the investigator from the time of first dose until progression is met, death or subsequent anticancer therapy is administered regardless of tolerability or duration on treatment. It includes the following 4 attributes:

- Population: Participants with unresectable advanced and/or recurrent ALK-positive NSCLC with resistance or intolerance to at least 1 prior ALK inhibitor treatment as defined by the inclusion and exclusion criteria, and who receive at least one dose of lorlatinib
- Variable: Confirmed Objective Response (OR) according to RECIST 1.1 per investigator, defined as confirmed partial response (PR) or confirmed complete response (CR) from the date of first dose until progressive disease (PD), death, or start of new anticancer therapy
- Intercurrent event: All data after the intercurrent event "start of subsequent anticancer therapy" will be excluded. All tumor assessments are considered regardless of gaps in assessments. Treatment interruptions is not an intercurrent event.
- Population-level summary: ORR, ie percentage of participants with confirmed CR or confirmed PR and corresponding 95% confidence interval (CI) based on Wilson's Score Method.

Another secondary estimand is the durability of treatment effect of Lorlatinib as assessed by the investigator from the time of first response until progression is met, death or subsequent anticancer therapy is administered regardless of tolerability or duration on treatment for participants showing a confirmed OR per investigator. It includes the following 4 attributes:

- Population: Participants with unresectable advanced and/or recurrent ALK-positive NSCLC with resistance or intolerance to at least 1 prior ALK inhibitor treatment as defined by the inclusion and exclusion criteria, who receive at least one dose of lorlatinib and showing a confirmed OR per investigator
- Variables: DoR

- Intercurrent event: All data after the intercurrent events "start of subsequent anticancer therapy" or "extended gap in tumor assessment prior to progression or death" will be excluded. Treatment interruptions is not an intercurrent event.
- Population-level summary: Kaplan-Meier Median of DoR and 2-sided 95% CI

Another secondary estimand is the intracranial treatment effect of Lorlatinib as assessed by the investigator from the time of first dose until intracranial progression is met per investigator, death or subsequent anticancer therapy is administered regardless of tolerability or duration on treatment. It includes the following 4 attributes:

- Population: Participants with unresectable advanced and/or recurrent ALK-positive NSCLC with resistance or intolerance to at least 1 prior ALK inhibitor treatment as defined by the inclusion and exclusion criteria, who receive at least one dose of lorlatinib and having Central Nervous System (CNS) metastases at study entry
- Variable: Confirmed Intracranial-Objective Response (IC-OR) according to RECIST 1.1
 per investigator, defined as confirmed Intracranial Partial Response (IC-PR) or
 Intracranial Complete Reponse (IC-CR) from the date of first dose until PD, death, or start
 of new anticancer therapy
- Intercurrent event: All data after the intercurrent event "start of subsequent anticancer therapy" will be excluded. All tumor assessments are considered regardless of gaps in assessments. Treatment interruptions is not an intercurrent event.
- Population-level summary: IC-ORR, ie percentage of participants with confirmed IC-CR or confirmed IC-PR and corresponding 95% confidence interval based on Wilson's Score Method.

Another secondary estimand is the durability of intracranial treatment effect of Lorlatinib as assessed by the investigator from the time of first intracranial response until intracranial progression is met, death or subsequent anticancer therapy is administered regardless of tolerability or duration on treatment for participants showing a confirmed IC-OR per investigator. It includes the following 4 attributes:

- Population: Participants with unresectable advanced and/or recurrent ALK-positive NSCLC with resistance or intolerance to at least 1 prior ALK inhibitor treatment as defined by the inclusion and exclusion criteria, who receive at least one dose of lorlatinib, having CNS metastases at study entry and showing a confirmed IC-OR per investigator
- Variable: IC-DoR according to RECIST 1.1 per investigator
- Intercurrent event: All data after the intercurrent events "start of subsequent anticancer therapy" or "extended gap in tumor assessment prior to progression or death" will be excluded. Treatment interruptions is not an intercurrent event.
- Population-level summary: Kaplan-Meier Median of IC-DoR and 2-sided 95% CI

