3.2.2. Confirmed Intracranial Objective Response Rate (IC-ORR)

Intracranial OR based on investigator assessment is defined as IC-CR or IC-PR according to RECIST v1.1 from date of first dose until documented Intracranial Progressive Disease (IC-PD) or start of new anticancer therapy without regard to discontinuation from treatment. Both

IC-CR and IC-PR must be confirmed by repeat assessments performed no less than 4 weeks after the criteria for response are first met. Participants without IC-CR or IC-PR or with death prior to first post-baseline assessment, inadequate baseline assessment, new anticancer therapy started prior to first post-baseline assessment, and all post-baseline disease assessments missing will be considered as non-responders.

IC-ORR is defined as the percent of participants with intracranial response (ie, best overall intracranial response as confirmed CR or confirmed PR considering only intracranial lesions) relative to participants with CNS metastases at study entry.

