6.2. Secondary Endpoints

6.2.1. Confirmed OR

Analysis set: Safety: All enrolled participants who take at least 1 dose of Lorlatinib **Analysis methodology**:

• Objective Response Rate (ORR) defined as the percentage of participants with a confirmed best overall response (BOR) of CR or PR according to RECIST v1.1. BOR will be determined based on reported overall responses at different evaluation timepoints by the investigator from the date of treatment start until documented

disease progression or start of new anticancer therapy, according to the following rules:

- CR = at least two determinations of CR at least 4 weeks apart and documented before progression and start of new anticancer therapy
- PR = at least two determinations of PR or better (and not qualifying for a CR) at least 4 weeks apart and before progression and start of new anticancer
- o SD (for participants with at least one measurable lesion at baseline) = at least one SD assessment (or better and not qualifying for CR or PR) ≥ 6 weeks after date of treatment start and before progression and the start of new anticancer therapy
- Non-CR/Non-PD (for participants with only non-target disease at baseline) = at least one Non-CR/Non-PD assessment (or better and not qualifying for CR ≥ 6 weeks after date of treatment start and before progression and the start of new anticancer therapy
- o PD = progression ≤ 13 weeks after date of treatment start and not qualifying for CR, PR or SD
- O Not Evaluable (NE) = all other cases.

Clinical deterioration will not be considered as documented disease progression.

- participants without documented CR or PR will be considered as non-responders
- 95% CI interval for ORR using the Wilson's Score method

Intercurrent events and missing data:

- data on response after subsequent anticancer therapy is administered will be excluded
- participants with death prior to first post-baseline assessment, inadequate baseline
 assessment, new anticancer therapy started prior to first post-baseline assessment, and
 all post-baseline disease assessments missing will also be considered as nonresponders.

Summaries used for reporting:

- The frequency (number and percentage) of participants with BOR of CR, PR, SD, PD, non-CR/non-PD (applicable only to participants with non-measurable disease at baseline), and NE (not evaluable)
- ORR estimated by dividing the number of participants with OR (CR or PR) by the number of participants in the safety set

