6.2.2. Confirmed IC-OR

Analysis set: Participants with CNS metastases based on Investigator Assessment

Analysis methodology:

The IC-OR will be summarized similar to OR (as described above in section 6.2.1), in Safety Population with CNS metastases based on investigator assessment. Surgery or radiotherapy of extracranial lesions will not affect the determination of IC-OR.

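### The IC-OR variable in SAP 2.1.2 ends at any progression, while its own lead sentence and SAP 3.2.2 end at intracranial progression, so some participants' response status depends on which line is programmed

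*SAP*

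**What the plan says.** The SAP describes the end of the intracranial response window in four places.

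- **SAP 2.1.2, intracranial response estimand, lead sentence.** The effect is followed "from the time of first dose until intracranial progression is met per investigator, death or subsequent anticancer therapy is administered".
- **SAP 2.1.2, same estimand, Variable attribute.** A confirmed IC-PR or IC-CR counts "from the date of first dose until PD, death, or start" of new anticancer therapy. The progression is not qualified as intracranial.
- **SAP 3.2.2, endpoint definition.** The window runs "until documented Intracranial Progressive Disease (IC-PD) or start of new anticancer therapy without regard to discontinuation from treatment".
- **SAP 6.2.2, analysis method.** "The IC-OR will be summarized similar to OR (as described above in section 6.2.1"). In 6.2.1 the CR rule is "at least two determinations of CR at least 4 weeks apart and documented before progression and start of new anticancer therapy", and the PR rule is parallel. Section 6.2.2 adds that extracranial surgery or radiotherapy leaves IC-OR unaffected. It does not mention extracranial progression.

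The unqualified abbreviation has a fixed meaning. It is introduced in the overall response estimand of SAP 2.1.2 as "from the date of first dose until progressive disease (PD), death, or start of new anticancer therapy", and SAP Appendix 1 lists PD and IC-PD as separate terms.

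Three related provisions bear on the intended meaning. Protocol 9.4.2 and SAP 3.2.2 restrict best intracranial response to lesions inside the brain. The IC-DoR estimand in SAP 2.1.2 runs to intracranial progression. SAP 6.2.4 takes progression in the brain lesions, or death, as the IC-DoR event.

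**The concern.** Two stated rules for the same secondary endpoint can classify the same participant differently. Under the Variable attribute, disease outside the brain can end the window in which an intracranial response may be confirmed. Under the lead sentence and SAP 3.2.2 it cannot. The methods section, to which a programmer would turn, inherits the overall-response rule without adapting it, so it does not settle the matter.

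The affected situation is realistic. The Schedule of Activities puts body imaging and brain MRI on one schedule, every 12 weeks ± 1 week, with no separate confirmation visit. The confirming brain scan may therefore come from the same visit at which extracranial progression is found. SAP 5.2.6 uses the investigator's assessment date for each nominal timepoint, so the two findings may carry one date.

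Two things are at stake: the numerator of IC-ORR, and membership of the IC-DoR analysis set, which consists of confirmed intracranial responders. With the any-PD rule, entry to the IC-DoR set would depend on extracranial disease while the IC-DoR event would not. In an open-label single-arm study it is better that this choice is not left until the data are visible.

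**Working it through.** The plan states no figure on this point, so the check compares the rules on specific scan histories and then works out the effect of one reclassified participant.

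**Rules compared**

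- Rule A: the SAP 2.1.2 Variable attribute (stop at any PD), with the 6.2.1 requirement that both determinations precede progression.
- Rule B: the SAP 2.1.2 lead sentence and SAP 3.2.2 (stop at intracranial PD).
- Common to both: confirmation at least 4 weeks after first response (SAP 3.2.2), and response data after new anticancer therapy excluded (SAP 2.1.2).

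**Scan histories (constructed for illustration)**

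| History | Rule A | Rule B |
|---|---|---|
| 1. IC-PR at week 12; at week 24 IC-PR again and extracranial PD on the same date; no new therapy | One determination before PD: non-responder | Two determinations 12 weeks apart, no IC-PD: responder |
| 2. IC-PR at week 12; extracranial PD between week 12 and a later brain scan that again shows IC-PR; no new therapy | Non-responder | Responder |
| 3. IC-PR at week 12, confirmed on an extra scan at week 16; extracranial PD at week 24 | Responder | Responder |
| 4. IC-PR at week 12; IC-PD at week 24 | Non-responder | Non-responder |
| 5. IC-PR at week 12; new anticancer therapy before the confirming scan | Non-responder | Non-responder |

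The rules split only in histories 1 and 2. In history 1, the 2.1.2 Variable taken alone is unclear, because a window ending at PD might include the PD date. The requirement in 6.2.1 that responses come before progression is what excludes the week 24 scan. In history 2 the rules split on either reading, but a brain scan after the extracranial PD must exist. Protocol 7.1 provides an end-of-treatment assessment only if more than 6 weeks have passed since the last evaluation.

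**Size per participant**

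The denominator of IC-ORR is the number n of treated participants with CNS metastases at study entry. It is the same under both rules. Moving one participant from responder to non-responder changes IC-ORR by 100 × 1/n percentage points. The documents plan 100 treated participants but give no n, so n is assumed:

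- n = 30: 100/30 = 3.3 points
- n = 40: 100/40 = 2.5 points
- n = 50: 100/50 = 2.0 points

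For scale, take n = 40 with 22 responders under Rule B (an assumed count): 22/40 = 55.0%, Wilson 95% CI 39.8% to 69.3%. With one participant reclassified, 21/40 = 52.5%, CI 37.5% to 67.1%. Rule A can lower the numerator or leave it unchanged, but cannot raise it.

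**The case against.** The strongest reply is that the SAP, read as a whole, already points to intracranial progression. The Variable attribute is the only place that names unqualified PD for this endpoint. Against it stand the lead sentence of the same estimand, the endpoint definition in 3.2.2, the restriction to intracranial lesions in the protocol and SAP, and the IC-DoR event in 6.2.4. The attribute looks like wording carried over from the overall response estimand. A careful programmer would probably use IC-PD. This stands, and it is why the point concerns an inconsistency and not an error that will certainly reach the results. It does not remove the inconsistency, because 6.2.2 leaves the inherited progression rule unqualified.

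Second, confirmation need not fall on the next 12-weekly scan. Any assessment at least 4 weeks later will do, and SAP 5.2.10 uses unscheduled tumor assessments for best overall response. This also stands: history 3 shows that an earlier confirming scan makes the two rules agree. Coincidence with extracranial PD is possible under the schedule, not inevitable.

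Third, a reader might infer that the plan biases IC-ORR downward by a calculable amount. Assuming a 55% response rate and 5% to 20% of responders affected gives losses of 0.55 × 5 = 2.75 to 0.55 × 20 = 11 points. The documents do not support this. They give no rate of extracranial-only PD at the confirming scan and do not show that the any-PD rule will be applied. The 55.6% in the protocol's Background comes from 9 patients with measurable brain lesions, whereas the denominator here is all participants with CNS metastases.

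**Conclusion.** The inconsistency is real and lies in the current text: within SAP 2.1.2 (lead sentence against Variable attribute) and between that attribute and SAP 3.2.2, with SAP 6.2.2 leaving it open. It matters for a participant with two intracranial responses at least 4 weeks apart, extracranial-only PD at or before the confirming brain scan, and no new anticancer therapy. Under the any-PD wording that participant is a non-responder and drops out of IC-DoR, which conflicts with an endpoint limited to intracranial lesions.

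The size is 2.0 to 3.3 points of IC-ORR per such participant for an assumed 50 down to 30 participants with CNS metastases. How many there would be cannot be derived from the documents, so the downward effect is conditional on the any-PD rule being used and no expected bias can be given.

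The consequence is confined to descriptive secondary endpoints, IC-ORR and IC-DoR. The primary adverse event endpoint and the sample size are untouched. The wording should be corrected because the conflict can change a participant's classification and removing it is nearly free.

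**What to change.** 1. In the Variable attribute of the intracranial response estimand (SAP 2.1.2), replace PD with IC-PD as the end of the window, matching the lead sentence and SAP 3.2.2.
2. In SAP 6.2.2, add a sentence saying that, for IC-OR, progression in the best-overall-response rules of 6.2.1 means IC-PD. It follows that a brain assessment on or after the date of extracranial-only PD counts toward confirmation, provided that no new anticancer therapy has started.

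The cost is two wording changes in the SAP. They need no additional scans, visits or data collection, and no change to the primary endpoint or its analysis. They should be made before the response data are reviewed.
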